5.4.3. ANALYSIS OF THE SECONDARY ENDPOINTS(S)

1. Description of histologic performance. The mean histologic adequacy score, total histologic area (mm²), alveolated area (mm²), open alveoli percent, percent crush artifact, and artifact free lung parenchyma percent will be reported as mean (+/- SD) or Median (Range). This data will be used for statistical planning for future trials.
2. Procedural characteristics such as activation time, procedure time, number of biopsies taken and type of airway (proportion used LMA, ETT, rigid bronchoscope) used will be reported as mean (+/- SD) or Median (Range). Logistic regression will be used to determine if procedural characteristic significantly affect the presence of a significant adverse event (primary outcome). Additionally, linear regression will be used to determine if any of the procedural characteristics effect histologic performance characteristics.
3. Diagnostic yield of cryobiopsy will be calculated as the proportion of patients for which cryobiopsy led to a specific diagnosis. A biopsy will be considered diagnostic, if it results in a specific diagnosis, either malignant or benign (granuloma, inflammation, fibrosis, infection) will be assumed to be a true positive.

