2.1. OBJECTIVE AND PURPOSE

The objective of this study is to evaluate the safety profile of the new 1.1mm single-use flexible cryoprobe with oversheath for the sampling of lung tissue. The safety profile will be assessed across the

various indications for transbronchial lung biopsy (i.e. lung transplant rejection surveillance, lung nodule biopsy, diffuse parenchymal lung disease, pneumonitis). Safety will be assessed by collecting AE and SAE information up to 30 days.

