be placed in saline. The removal tool accompanying each cryoprobe can be used to carefully remove the specimen from the tip of the cryoprobe only after the specimen was defrosted. Specimens will then be transferred into a fixative (i.e. formalin) per institutional policy and sent to the local institutional pathology lab for processing and interpretation. Each biopsy sample will then be sent for central pathology interpretation. If tissue cultures are clinically indicated, an additional specimen may be placed in sterile saline

For non-lung transplant rejection related biopsies, a minimum of 3 biopsies must be taken using the 1.1mm sheath cryoprobe. For lung transplant rejection surveillance biopsies, a minimum of 5 cryobiopsies must be taken (more if needed), as per IHS LT guidelines, at least 5 pieces of well-expanded alveolated lung parenchyma are required for an assessment of acute rejection.⁹ As part of this study, only cryobiopsy with the 1.1mm single-use flexible cryoprobe with oversheath is permitted for transbronchial lung biopsy. This excludes the use of needle, forceps, and brush biopsy. In case of cryoprobe failure a new 1.1mm sheath cryoprobe should be used. A bronchoalveolar lavage or wash is allowed if clinically indicated but must be performed after the index procedure is performed.

Following the procedure, the patient will be returned to the post-anesthesia care unit and a post-procedural chest x-ray will be obtained and results will be documented.

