5. STATISTICAL CONSIDERATIONS

5.1. STATISTICAL AND ANALYTICAL PLANS

The study is not powered to make a statistical conclusion due to the small sample size and the safety phase in which the treatment is. As the true safety profile of the 1.1mm flexible single-use cryoprobe with oversheath is not known, we will base our statistical plan based on current standard method for transbronchial biopsy, forceps biopsy.

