5.4. DESCRIPTION OF STATISTICAL METHODS

5.4.1. GENERAL APPROACH

This is a multi-centered, prospective, single arm trial aimed at establishing the safety profile of a novel 1.1mm flexible single-use cryoprobe with oversheath. Secondary outcomes will be descriptive procedural characteristics that will be used to power future trials.

All continuous data will be presented as means with standard deviations. Categorical data will be represented by percentages. Statistical comparisons will be made using linear and logistic regression

analysis where applicable. Sensitivity, specificity, positive and negative predictive value and accuracy of all procedures will be calculated.

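### The regressions in 5.4.3 item 2 have no term for indication, although section 3.4 sets the minimum number of biopsies by indication, so a difference between indications can be reported as an effect of biopsy number

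*Combined protocol and SAP*

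**What the plan says.** Section 5.4.3 item 2 names the predictors: "Procedural characteristics such as activation time, procedure time, number of biopsies taken and type of airway". For SAE it states: "Logistic regression will be used to determine if procedural characteristic significantly affect the presence of a significant adverse event (primary outcome"). For the histology measures of item 1 it states: "linear regression will be used to determine if any of the procedural characteristics effect histologic performance characteristics". The general statement in 5.4.1 is only this: "Statistical comparisons will be made using linear and logistic regression" analysis where applicable. Neither section names an adjustment covariate or a stratification, or says whether the models have one predictor or several.

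Section 3.4 links one of these predictors to the reason for the biopsy: "For non-lung transplant rejection related biopsies, a minimum of 3 biopsies must be taken using the 1.1mm sheath cryoprobe", and "For lung transplant rejection surveillance biopsies, a minimum of 5 cryobiopsies must be taken (more if needed"). Section 2.1 enrols a mixed population and intends safety to be assessed across the "various indications for transbronchial lung biopsy (i.e. lung transplant rejection surveillance, lung nodule biopsy, diffuse parenchymal lung disease, pneumonitis"). Section 5.2 refers to disease states for description. Neither statement is carried into the models.

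On inferential status, 5.1 says: "The study is not powered to make a statistical conclusion due to the small sample size".

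**The concern.** The number of biopsies partly identifies the indication, because the protocol makes it so. Indication may also bear on the outcomes. Several histology measures score alveolar tissue (alveolated area, open alveoli percent, artifact-free parenchyma). Section 3.4 says surveillance biopsies must yield alveolated parenchyma, and section 3.6 gives transplant surveillance as its example of a CT without specific abnormality, whereas nodule patients have a lesion as target. A difference between indications, in tissue or in risk, is therefore plausible.

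If there is one, a model with biopsy number and without indication attributes part of it to the number of biopsies. The wording of item 2 is causal and speaks of significance, so the finding could be read as advice on technique: that taking more samples changes tissue quality or harm. Procedure time may carry the same bias, since more biopsies should take longer.

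**Working it through.** **Inputs from the documents.** 50 participants (5.7); minimum 3 or 5 biopsies (3.4). There is no figure of the plan to reproduce: 5.7 gives 50 without alpha, power, effect size or SD, and nothing is given for the regressions.

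**Assumptions, not in the documents.** 10, 17 or 25 of the 50 are transplant patients (share p = 0.20, 0.34, 0.50). Number of biopsies = minimum + Poisson extra with mean m = 0.8 or 2. There is one normally distributed histology value per patient. The transplant/other difference is d = 0 to 1 SD. The true effect of biopsy number is zero.

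**Step 1: how closely number follows indication.** Number = 3 + 2T + extra, where T = 1 for transplant. The variance due to indication is 4p(1-p) and the rest is m, so r² = 4p(1-p) / [4p(1-p) + m].
- Weakest setting (p = 0.20, m = 2): 0.64/2.64 = 0.24, r = 0.49.
- Strongest setting (p = 0.50, m = 0.8): 1/1.8 = 0.56, r = 0.75.
- With a tighter spread (p = 0.50, m = 0.5): 1/1.5 = 0.67, r = 0.82.

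**Step 2: size of the spurious slope.** With no true effect, the expected unadjusted slope per biopsy is d × 2p(1-p) / [4p(1-p) + m]. At d = 1 SD it is 0.32/2.64 = 0.12 SD in the weakest setting and 0.5/1.8 = 0.28 SD in the strongest.

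**Step 3: how often the linear model declares number significant** (two-sided 5%, 20,000 simulated trials per cell, no indication term):

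| Transplant patients | Mean extra | d = 0 | d = 0.5 SD | d = 1.0 SD |
|---|---|---|---|---|
| 10 | 2 | 4.6% | 10.2% | 25.5% |
| 10 | 0.8 | 5.1% | 15.1% | 43.1% |
| 17 | 2 | 5.0% | 14.4% | 40.3% |
| 17 | 0.8 | 5.1% | 21.5% | 63.3% |
| 25 | 2 | 5.0% | 16.4% | 46.4% |
| 25 | 0.8 | 4.9% | 25.1% | 69.8% |

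Shorter runs of the same grid put the outer ends at 9% and 72%, so the ranges are quoted as about 9-25% and 25-72%. At d = 0.2 SD the rate is only 6-8%. With T in the model it is 4-6% throughout.

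**Step 4: the SAE model.** This uses a likelihood-ratio test, half the patients transplant, mean extra 0.5 or 1, and assumed SAE rates (other versus transplant). Without indication, number is declared significant in about 7% of trials at 10% versus 10%, 11-16% at 5% versus 15%, and 26-32% at 10% versus 30%. With a transplant/other term the rate is about 5-7% in these settings; the small excess over 5% reflects few events. At 5% versus 15% only 25 × 0.05 + 25 × 0.15 = 5 events are expected.

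**Step 5: price of adjustment.** The variance inflation for biopsy number is 1/(1 - r²) = 1 + 4p(1-p)/m. On the grid of Step 3 it runs from 1 + 0.64/2 = 1.32 to 1 + 1/0.8 = 2.25. Intervals are therefore roughly √1.32 = 1.15 to √2.25 = 1.5 times as wide, ignoring any fall in residual variance.

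**The case against.** The strongest reply is that the bias is conditional and its size rests on unsupported inputs. That stands. No section gives a difference in histology or SAE risk between indications, the transplant share, or the spread of extra biopsies. With no difference the unadjusted test behaves correctly, and with a small one the harm is slight.

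Several stronger readings are tempting and go too far:
- *Number is fixed by indication.* Section 3.4 sets minimums, with no maximum. The confounding is partial, and an adjusted effect can be estimated.
- *All the technique findings are compromised.* The protocol links only biopsy number to indication, and procedure time follows plausibly. No such link is documented for activation time or airway type.
- *The biased coefficients will feed future trial designs.* The planning sentences in 5.2, 5.4.1 and 5.4.3 item 1 concern descriptive data. None says that regression coefficients will be used.
- *A false positive somewhere is nearly certain.* Four characteristics by seven outcomes gives 28 tests and 1 - 0.95^28 = 76%. That needs independence and one test per pair. The outcomes overlap (alveolated area is part of total area), the list of characteristics is open-ended, and the form of the models is not stated. The figure is illustrative at most and carries no weight here.

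It is also fair to say that the true effect of number need not be zero for every outcome. Total and alveolated area would rise with number if summed per patient, and the plan does not state the unit of analysis.

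Finally, 5.1 already disclaims statistical conclusions. That lowers the stakes, but it does not remove the conflict with item 2, which sets out to establish significance. Nor does low power excuse omitting a known, protocol-made confounder.

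**Conclusion.** The point holds in conditional form. The protocol links biopsy number to indication and the planned models ignore indication, so a difference between indications *can* be reported as an effect of biopsy number, and plausibly of procedure time. A reader might infer that it *will* be. The documents do not support that, because they do not show that outcomes differ by indication.

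Under the stated assumptions the false-positive rate for biopsy number in the linear model is about 5% at no difference, 9-25% at 0.5 SD and 25-72% at 1.0 SD, against 4-6% with an indication term. The SAE model shows the same pattern under assumed event rates. These are secondary, exploratory analyses: the primary SAE proportion in 5.4.2 and its 30% criterion are unaffected. The change is still worth making, because the better model is clear and cheap.

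**What to change.** In 5.4.3 item 2:
- **Linear models.** Include indication, at least as transplant surveillance versus other, or report results within indication. State whether the unit is the patient or the specimen.
- **SAE.** Include at most a transplant/other term, with penalised estimation if events are few, or replace the model by descriptive tables by indication. A four-level indication factor would be too much for the number of events likely among 50 patients.
- **Wording.** Report estimates with 95% CIs as exploratory associations, and delete *significantly* and the causal verbs, in line with 5.1.

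The cost is SAP wording and a degree of freedom or a few. Little new data should be needed: the site must know the indication to apply the minimum in 3.4, and 3.6 already collects nodule target, diffuse CT pattern or absence of a specific abnormality. One explicit indication field would settle it. The statistical price is wider intervals for biopsy number, because less variation in number remains within indication. That width is an honest statement of what 50 patients can show.

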2.4. STUDY SITE PARTICIPATION

This study will require a minimum of two participating sites. Each site will have a sufficient patient population to enroll 20-30 subjects over the enrollment period (3 months). Each site must have sufficient transbronchial biopsy volume (defined as at least 100 cases per year). To ensure adequate access to patients across the various indications for transbronchial biopsy, each site must have institutional centers for Lung Cancer, Lung Transplantation and Interstitial Lung Disease. In addition, the principal investigator and each participating co-investigator at each site must have cryobiopsy experience, defined as completion of at least 10 cryobiopsies.

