3.3. SEDATION/AIRWAY

Patients will undergo the procedure under deep sedation with an artificial airway (endotracheal tube, laryngeal mask airway or tracheostomy) in place. The use of a rigid bronchoscope will be left to the discretion of the physician performing the procedure. Deep sedation medications and route of administration are at the discretion of the sedating physician.

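### The planned regression of histology on procedural characteristics names no site term, so a difference between the two sites could be reported as an effect of technique (minor)

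*Combined protocol and SAP*

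**What the plan says.** Section 5.4.3, item 2 first describes the predictors: "Procedural characteristics such as activation time, procedure time, number of biopsies taken and type of airway". It then states that "linear regression will be used to determine if any of the procedural characteristics effect histologic performance characteristics". The only other statement about the model is in section 5.4.1: "Statistical comparisons will be made using linear and logistic regression", where applicable. Neither section names a site term, a stratification or any covariate.

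Four other parts of the document bear on this analysis:

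- **Sites.** Section 2.4 says "This study will require a minimum of two participating sites" and "Each site will have a sufficient patient population to enroll 20-30 subjects over the enrollment period". The synopsis gives two sites and section 5.7 sets a total of 50 patients.
- **Tissue handling.** Section 3.4 has specimens placed in fixative "per institutional policy and sent to the local institutional pathology lab for processing" and interpretation, after which they go for central reading. Section 3.6 has one pathology core lab review every case.
- **Airway.** Section 3.3 allows an endotracheal tube, a laryngeal mask or a tracheostomy, and adds: "The use of a rigid bronchoscope will be left to the discretion of the physician performing the procedure".
- **Freeze time.** Section 3.4 starts at 4 seconds and lets the bronchoscopist extend it after inadequate tissue.

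**The concern.** A central read removes differences between readers. It cannot remove differences that fixation, embedding or sectioning has already put into the tissue, and area, open alveoli and crush artifact are all measured on that tissue. The outcome could therefore carry a site component that has nothing to do with the procedure.

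Technique could carry one too, because discretionary choices follow operators' habits and each operator works at one of the two sites. A regression over all 50 patients without a site term mixes the comparison within sites with the comparison between them. If one site's laboratory yields larger or less crushed sections, whatever airway that site favours would seem to improve the biopsy.

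At stake is the accuracy of a secondary, exploratory finding about technique. This problem would remain with a single histology value per patient and within a single indication.

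**Working it through.** **No plan figure to reproduce.** Section 5.7 sets 50 patients by judgement. The document gives no effect size, alpha or power for this regression, no between-site variance and no airway use by site. What follows is an illustration under stated assumptions.

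**Inputs from the document.** Two sites; 20-30 patients per site (section 2.4); 50 in total (section 5.7).

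**Assumptions.** One histology value per patient; 25 patients per site; a binary predictor such as airway type, with no true effect; two-sided alpha 5%. The site difference is either random (ICC 0.05, total variance 1) or fixed (0.5 SD, residual SD 1). Use of the characteristic is p at site A and 1 − p at site B.

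**Step 1: spurious effect.** With equal sites, a fraction p of users and 1 − p of non-users are at site A. For a fixed site shift d, the model without site therefore estimates

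d × [p − (1 − p)] = d × (2p − 1).

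For d = 0.5 this gives:

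- 70/30: 0.5 × 0.4 = 0.20 SD
- 80/20: 0.5 × 0.6 = 0.30 SD
- 90/10: 0.5 × 0.8 = 0.40 SD

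Simulation gives 0.21, 0.31 and 0.40.

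**Step 2: false-positive rate by hand at 80/20, d = 0.5.**

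- Residual variance without site: 1 + d² × p(1 − p) = 1 + 0.25 × 0.16 = 1.04.
- Standard error: √1.04 × 2/√50 = 0.288.
- Bias divided by standard error: 0.30/0.288 = 1.04.
- With critical value 2.01, the normal approximation gives P(Z > 0.97) + P(Z < −3.05) ≈ 17%.

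**Step 3: simulation.** Ordinary least squares with and without a site indicator, at least 8,000 runs per cell:

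| Use at site A / site B | No site term, ICC 0.05 | No site term, fixed 0.5 SD | Site term, either case |
|---|---|---|---|
| 50/50 | about 5% | about 5% | about 5% |
| 70/30 | about 7% | about 11% | about 5% |
| 80/20 | about 10% | about 18% | about 5% |
| 90/10 | about 14% | about 28% | about 5% |

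The 18% agrees with the hand result of 17%.

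**Step 4: sensitivity.**

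- At 80/20, ICC from 0.01 to 0.10 gives about 6% to 16%.
- At 60/40 and ICC 0.05 the rate is 5.4%.
- A fixed shift of 0.2 SD gives about 6% at 70/30 and 7% at 80/20.
- A 20/30 split of patients with a 0.5 SD shift at 80/20 gives 17.3%, against 17.7% for 25/25.

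**Step 5: price of the site term.** The correlation between the characteristic and site is 2p − 1, so the standard error grows by about 1/√[1 − (2p − 1)²]: 1.09 at 70/30, 1.25 at 80/20 and 1.67 at 90/10. The simulated averages with no site shift are 1.11, 1.29 and 1.81. They are higher because chance makes the overlap within sites thinner in some samples.

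**The case against.** **Both conditions are assumed.** Bias needs a histology difference between sites and unequal use of the characteristic. The document reports neither, and mild values give almost no inflation. The central read and the minimum room temperature and gas pressure (section 3.6) also remove some variation. This stands, and it is why the figures are only illustrative. Nothing in the plan controls either condition, however.

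**The plan is silent rather than wrong.** No model is specified, so an analyst could still add site. That is fair: the gap is under-specification. Read plainly, though, the text describes an unadjusted regression.

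**The analysis has little weight.** Section 5.1 says the study is not powered for a conclusion. That lowers the stakes, but low power does not remove confounding, and item 2 is still worded as determining whether technique changes histology.

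**The illustration is narrow.** It fits airway type. Activation time, procedure time and number of biopsies are not binary.

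Two stronger readings are tempting, and the document supports neither:

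- A reader might infer that biased coefficients would feed into future trial designs. Sections 5.2, 5.4.1 and 5.4.3 (item 1) tie future planning to the descriptive data, not to the regression coefficients.
- A reader might infer that each site sets its own airway policy. Section 3.3 gives the physician discretion over the rigid bronchoscope only, and does not say who chooses among the other airways. That habits cluster by site is an inference.

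**Conclusion.** The concern holds as a minor point. Section 5.4.3, item 2 leaves site out of a two-site regression whose outcome is measured on locally processed tissue and some of whose predictors are discretionary. If histology and technique both differ by site, a site difference can be reported as an effect of technique.

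For a binary predictor under the assumptions above, the false-positive rate runs from nominal with equal use to about 14% (ICC 0.05) or 28% (0.5 SD shift) at 90/10. The true size cannot be known from the document.

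Nor does a site term make the coefficients causal. Freeze time is extended because earlier tissue was inadequate, so poor tissue can lead to longer freezing. The minimum number of biopsies depends on indication: 5 for transplant surveillance and 3 otherwise (section 3.4). Site adjustment removes neither problem. The primary safety endpoint and its 30% criterion are untouched.

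**What to change.** In section 5.4.3, item 2:

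1. State that the linear regressions of histology on procedural characteristics include site as a fixed effect.
2. Tabulate each histology measure and each procedural characteristic by site.
3. Where a characteristic is used almost only at one site, report it descriptively as not separable from site.
4. Describe the results as exploratory associations, and note the limits for freeze time and number of biopsies.

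The cost is a few sentences and one degree of freedom. Site is already known for every patient, so no new data are needed. Intervals widen where use tracks site: the standard error is about 1.1 times as large at 70/30, 1.3 times at 80/20 and 1.8 times at 90/10. That loss reflects how little information about technique exists within sites in such a case.

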5.5. PLANNED INTERIM ANALYSES

Out of an abundance of caution for safety, following each 10 consecutively completed cases, the serious adverse event rate will be calculated. This data will only be available to the DSMB for review.

5.6. SAFETY REVIEW

After any serious adverse event, a safety review will take place and recruitment at all sites will be halted. The DSMB will meet to review the case and overall safety of the trial, once adjudicated by the DSMB, the trial can be resumed.

5.7. SAMPLE SIZE

This is a safety study. The goal of this study is to identify any high frequency adverse events, as well as collect preliminary data on the potential efficacy of the novel 1.1mm flexible single-use cryoprobe with oversheath. As no current data exists to accurately estimate the variance in SAE rates, there is no reliable data to power this study. We conservatively estimate that a stable estimation will of the SAE rate will occur after 50 cases. Thus in this initial study, we will include 50 participants.

